4 STUDY SUBJECTS

4.1 Analysis sets

The list of subjects to be included in each of the analysis sets is to be agreed between the Syne qua non statistician and Blue Earth Diagnostics once all study data are available and prior to database lock.

Enrolled Set: All subjects who entered screening.

Safety Analysis Set (SAF): All subjects who have been included in the database and have been administered ^{18}F -fluciclovine will be included in the Safety Analysis Set (SAF).

Full Analysis Set (FAS): All subjects enrolled who have had an ^{18}F -fluciclovine PET/CT scan will be included in the Full Analysis Set (FAS).

Evaluable Analysis Set (EAS): All subjects from the FAS who have an intended treatment management plan completed and a revised management plan page completed will be included in the Evaluable Analysis Set (EAS).

Per Protocol Set (PPS): All subjects in the EAS who meet the second and third protocol inclusion criteria (see protocol section 6.2) and any other subject without major significant deviation following review of the protocol deviation list.

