4.3 Protocol Deviations

Failed inclusion criteria and failed exclusion criteria will be listed for screening failures.

The number and percentage of subjects within each deviation category will be presented by deviation type (Major Significant, Major or Minor) and by site and overall. The deviation category and type will be provided by Blue Earth Diagnostics. All protocol deviations will be listed.

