5.4 Statistical Analysis

5.4.1 Primary Efficacy Analysis

The primary efficacy analysis will be based on the EAS and will be repeated on the PPS as a secondary analysis. Comparisons between the original treatment plan and the revised treatment plan will be categorised as no change, major change or other change. The definitions of the change categories are listed below.

- No change: the original treatment plan is the same as the revised treatment plan
- Major change: the original treatment plan is not the same as the revised treatment plan and the grouping for the original treatment plan is not the same as the grouping for the revised treatment plan

These will be further split and presented according to the following categories:

- Salvage or Non-curative systemic therapy to Watchful waiting
 - Salvage therapy to Non-curative systemic therapy
 - Non-curative systemic therapy to Salvage therapy
 - Alternative Major change
- Other change: the original treatment plan is not the same as the revised treatment plan but the grouping for the original treatment plan is the same as the grouping for the revised treatment plan

These will be further split and presented according to the following categories:

- Modified RT field plan
- Modified androgen-deprivation regimen
- Alternative Other change

Groupings of treatment plans are detailed in the following table:

Original Treatment Plan	Grouping for Original Tx Plan	Revised Treatment Plan	Grouping for Revised Tx Plan
Was androgen deprivation therapy planned	Androgen Deprivation Therapy	Androgen deprivation therapy	Androgen deprivation therapy
		Active surveillance	Active surveillance
		Chemotherapy	Chemotherapy
Salvage radiotherapy to the prostate bed	Salvage Radiotherapy	Salvage radiotherapy to the prostate bed	Salvage Radiotherapy
Salvage radiotherapy to the prostate bed, with boost to areas guided by conventional imaging		Salvage radiotherapy to the prostate bed, with boost to areas guided by conventional imaging	
		Salvage radiotherapy to the prostate bed with boost to areas guided by fluciclovine (18F) PET/CT	
Salvage radiotherapy to the prostate bed and whole pelvis	Salvage Radiotherapy	Salvage radiotherapy to the prostate bed and whole pelvis	Salvage Radiotherapy

Original Treatment Plan	Grouping for Original Tx Plan	Revised Treatment Plan	Grouping for Revised Tx Plan

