5.4.2.3 Detection rates

The detection rate (DR) will be calculated as $(\text{TP}+\text{FP})/n$ from the above table.

The point estimate (expressed in percentage) of the DR will be presented at the region level and at the subject level, as well as for the prostatic bed, other pelvic disease and distant metastases. These rates will be presented for all subjects from the FAS and PPS, overall and across a range of baseline PSA values:

- 0 – 0.2
- >0.2 – 0.5
- >0.5 – 1.0
- >1.0 – 2.0
- 2.0 – 5.0
- 5.0 – 10.0
- >10.0

to determine the optimum PSA threshold for lesion detection.

The detection rates will also be summarised across the following baseline Gleason score categories: ≤ 6 , 7, 8 and ≥ 9 .

All detection rate data will be listed.

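### SAP 4.1 words the Per Protocol Set as a union, so a subject who meets inclusion criteria 2 and 3 stays in despite a major significant deviation

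*SAP*

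**What the plan says.** SAP 4.1 defines the EAS by two conditions that must both hold: "All subjects from the FAS who have an intended treatment management plan completed and a revised management plan page completed". No deviation filter applies at that stage.

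The PPS follows in one sentence. Its first part is "All subjects in the EAS who meet the second and third protocol inclusion criteria (see protocol section 6.2"; its second is "and any other subject without major significant deviation following review of the protocol deviation list". In protocol section 6.2, criterion 2 is the PSA definition of suspected recurrence, and criterion 3 is negative or equivocal standard imaging in the previous 60 days.

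The PPS is used in three places:
- SAP 5.4.1: "The primary efficacy analysis will be based on the EAS and will be repeated on the PPS as a secondary analysis".
- SAP 5.4.2.2: the diagnostic performance summaries are repeated on it.
- SAP 5.4.2.3: "These rates will be presented for all subjects from the FAS and PPS".

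On deviations, SAP 4.3 names three types (Major Significant, Major, Minor) and adds: "The deviation category and type will be provided by Blue Earth Diagnostics". Neither document gives criteria for the top grade. SAP 4.1 also provides that membership lists are settled before database lock between the statistician and the sponsor.

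**The concern.** A per-protocol set normally removes subjects whose conduct or eligibility departs seriously from the protocol. Here the second clause speaks of any other subject, which can only mean someone whom the first clause has not already admitted. It therefore enlarges the set. A subject who meets criteria 2 and 3 has entered through the first clause, and nothing later in the sentence can remove him.

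The PPS is the only alternative set named for the primary analysis. If it keeps subjects with serious deviations, agreement between EAS and PPS says nothing about whether those deviations matter. The added subjects are also not clearly limited to the EAS. And a subject who fails criterion 2 or 3 comes back in if the failure is not graded Major Significant.

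**Working it through.** **1. Set logic.** Cross the two attributes and compare the printed rule (union) with the usual one (intersection), for EAS subjects:

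| Meets criteria 2 and 3 | Major significant deviation | Printed rule | Intersection |
|---|---|---|---|
| Yes | No | In | In |
| Yes | Yes | **In** | Out |
| No | No | **In** | Out |
| No | Yes | Out | Out |

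The rules differ in the two middle rows. The printed rule empties only the last.

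**2. Who can fall in the second row.** Protocol section 13 lists, among violations, use of a prohibited concomitant medication and use of an unvalidated camera or a different imaging technique. Protocol section 10.3 requires the treatment plan to be documented before the scan, while the EAS asks only that a plan be completed. None of these bears on criterion 2 or 3. The documents do not say how they would be graded; if graded Major Significant, the subject would still stay in the PPS.

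**3. The plan's own figures.** No size is stated for the PPS. The sample size does reproduce: at 89 positives and 30% the exact 95% interval is 0.207 to 0.406 (width 0.199). Then 89/0.40 = 222.5, so 223; the plan raises this to 248 to be 90% sure of enough positives; and 248/0.85 = 291.8, so 292. I take 248 as the illustrative EAS.

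**4. Count affected.** Let *d* be the share of the EAS with a major significant deviation and *m* the share of those who meet criteria 2 and 3. Both are assumptions. The printed rule keeps 248 × *d* × *m* subjects whom the intersection removes:

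| *d* | Deviators, 248 × *d* | Intersection PPS | Kept, *m* = 1 | Kept, *m* = 0.5 | Kept, *m* = 0 |
|---|---|---|---|---|---|
| 5% | 12.4 | 235.6 | 12.4 | 6.2 | 0 |
| 10% | 24.8 | 223.2 | 24.8 | 12.4 | 0 |
| 15% | 37.2 | 210.8 | 37.2 | 18.6 | 0 |

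The table takes the third row of the logic table as empty, meaning that every failure of criterion 2 or 3 is graded Major Significant. Each 1% of the EAS in that row would add 0.01 × 248 = 2.5 subjects.

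SAP 5.1 frames the primary variable in scan-positive subjects. At 40% positivity, the *m* = 1 counts become 0.40 × 12.4 = 5.0, 0.40 × 24.8 = 9.9 and 0.40 × 37.2 = 14.9, out of 0.40 × 248 = 99.2 positives, if deviators are positive as often as others.

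**5. Possible effect on the estimate.** If the overall change rate is 30% and deviators change at rate *r*, the rate without them is (0.30 − *d* × *r*)/(1 − *d*). For *d* = 10%:
- *r* = 0 gives 0.30/0.90 = 33.3%.
- *r* = 0.6 gives 0.24/0.90 = 26.7%.
- *r* = 1 gives 0.20/0.90 = 22.2%.

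The outer bounds are 31.6% and 26.3% at *d* = 5%, and 35.3% and 17.6% at *d* = 15%. With *m* = 1, the printed PPS would show none of this movement.

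**The case against.** The strongest reply is that this is a drafting slip in a secondary set, with safeguards around it. Membership is agreed subject by subject before lock, SAP 4.2 tabulates the size of each set, and SAP 4.3 lists every deviation. A PPS equal to the EAS despite recorded major significant deviations would be noticed. This stands in part. But agreeing a list does not supply a rule: it happens once all data are available in an open-label study, the sponsor supplies the grades, and SAP 4.2 plans individual membership and exclusion reasons for the evaluable set only.

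A second reply is that an intersection need not be the intention. The review may be meant to keep subjects whose failure of criterion 2 or 3 was trivial, such as imaging slightly outside the 60-day window. That is a legitimate choice and explains the third row of the logic table. It does not explain the second row.

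A third reply is that the lack of an explicit EAS limit hardly touches the primary repeat, because a subject without both plans cannot be classified as changed or unchanged. That is correct. The scope matters for the diagnostic and detection summaries, where a scanned subject without both plans could be counted.

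A reader might go further and infer that all subjects with a major significant deviation stay in, that the PPS must nearly equal the EAS, or that the repeat cannot test robustness at all. The documents support none of these. Subjects in the last row are removed. Protocol section 13 puts failure of the eligibility criteria first among its listed violations, so failures of criterion 2 or 3 could well carry the top grade. How close the PPS comes to the EAS depends on rates that are not given.

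**Conclusion.** The definition is wrong as printed, and no other section corrects it. It excludes only EAS subjects who both fail criterion 2 or 3 and have a major significant deviation. The PPS repeats stay informative about that group and are blind to major significant deviations in everyone else.

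The size is uncertain: from none to about 37 of 248 subjects over the assumed range, depending mainly on how many deviators meet criteria 2 and 3. The rates are illustrative, and the 30% and 40% are the plan's own assumptions.

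The EAS primary estimate, its confidence interval and the sample size are untouched, so this should be corrected before lock but does not threaten the main result.

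**What to change.** Before database lock, replace the PPS sentence in SAP 4.1 with an intersection, for example: *PPS: every EAS subject who satisfies inclusion criteria 2 and 3 of protocol section 6.2 and for whom the pre-lock deviation review records no major significant deviation.*

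If the sponsor deliberately wants to keep subjects with a trivial failure of criterion 2 or 3, the sentence should say so, limit them to the EAS, and still exclude every subject with a major significant deviation. In either case, write down what makes a deviation Major Significant before membership is agreed.

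The cost is one or two sentences and a smaller PPS. Interval width grows roughly as 1/√(1 − *d*). Starting from the plan's 0.199, losing 5%, 10% or 15% of subjects gives about 0.199 × 1.026 = 0.204, 0.199 × 1.054 = 0.210 or 0.199 × 1.085 = 0.216, in the PPS repeat only.

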4.2 Disposition of Subjects

The number and percentage of all subjects enrolled, included in each analysis set, who completed the study and who prematurely withdrew, including a breakdown of the primary reasons for withdrawal, will be presented.

All enrolled subjects will be listed indicating their membership to the evaluable analysis set along with the reason for exclusion.

Completion and withdrawal information will be listed, including individual reasons for withdrawal.

4.3 Protocol Deviations

Failed inclusion criteria and failed exclusion criteria will be listed for screening failures.

The number and percentage of subjects within each deviation category will be presented by deviation type (Major Significant, Major or Minor) and by site and overall. The deviation category and type will be provided by Blue Earth Diagnostics. All protocol deviations will be listed.

4.4 Background and Demographic Characteristics

4.4.1 Demographic and Baseline Characteristics

Demographic characteristics (age, ethnic origin and race collected at Screening), body measurements (height, weight collected and BMI derived at Visit 2) will be summarised for the enrolled set, FAS, EAS and PPS populations.

Body mass index (BMI) is calculated as $(\text{weight (kg)}/\text{height (m)}^2)$.

Individual demographic characteristics and body measurements data will be listed.

4.4.2 Medical History

Medical history events will be coded using the latest version of the Medical Dictionary for Regulatory Activities (MedDRA).

The number and percentage of subjects from the FAS with previous medical history and current events will be tabulated by system organ class (SOC), preferred term (PT). SOCs will be ordered in decreasing frequency of the total number of subjects with medical history events reported in each SOC and PTs will be ordered within a SOC in decreasing frequency of the total number of subjects with each medical history event.

All medical history events will be listed.

4.4.3 Prostate Cancer History

Details of prostate cancer history will be summarised for subjects from the FAS, and will consist of:

- Time since initial diagnosis (months), calculated as $[12 * (\text{date of informed consent} - \text{date of initial prostate cancer diagnosis} + 1) / 365.25]$
- TNM stage: Pathological TNM stage if available, otherwise Clinical TNM stage
- Gleason total score: Gleason total score from surgery if available, otherwise Gleason total score from biopsy
- Time since adjuvant treatment (months), calculated as $[12 * (\text{date of informed consent} - \text{stop date of adjuvant treatment} + 1) / 365.25]$
- Duration of adjuvant treatment (months), calculated as $[12 * (\text{stop date of adjuvant treatment} - \text{start date of adjuvant treatment} + 1) / 365.25]$
- Time since diagnosis of biochemical recurrence (BCR) in days, calculated as $(\text{date of informed consent} - \text{date of diagnosis of biochemical recurrence} + 1)$. Time since diagnosis of BCR may be derived in months if more appropriate.
- Baseline PSA value, baseline being defined as the last value prior to fluciclovine (^{18}F) administration

Details of prostate cancer history will be listed.

Date imputation for incomplete dates:

- If day part missing, use 15th of the month
- If day and month parts missing, use 01 July.

4.4.4 Cancer Therapies for Prostate Cancer

Cancer therapies for prostate cancer will be coded according to the latest version of the World Health Organization Drug Dictionary Enhanced (WHO DDE).

Cancer therapies will be categorised as follows:

Subjects with radical prostatectomy:

- Radiotherapy
- No radiotherapy

Subjects without radical prostatectomy:

- Radiotherapy only
 - EBRT only
 - Brachytherapy only
 - EBRT and brachytherapy
- Radiotherapy and other therapies
 - EBRT and other therapies
 - Brachytherapy and other therapies
- Other therapies

Prior cancer therapies for prostate cancer are defined as those for which the end date is prior to the date of injection of ^{18}F -fluciclovine.

Concomitant cancer therapies for prostate cancer are defined as those with a start date on or after the injection date of ^{18}F -fluciclovine, or those with a start date before the injection date of ^{18}F -fluciclovine but which continued with a stop date on or after the injection date of ^{18}F -fluciclovine.

If cancer therapy dates are incomplete and it is not clear whether the medication was concomitant, it will be assumed to be concomitant.

The number and percentage of subjects per category of prostate cancer therapy will be presented for all subjects from the SAF, separately for subjects with and without radical prostatectomy. This summary will be repeated for prior and concomitant cancer therapies.

All therapies for prostate cancer will be listed including type of therapy, reported therapy name, medication class, standardised medication name, dose, dose unit, route of administration, start date and end date or 'ongoing' flag, therapy comments.

4.4.5 Prior and Concomitant Medications

Prior and concomitant medications will be coded according to the latest version of the WHO DDE.

Prior medications are defined as those for which the end date is prior to the date of injection of ^{18}F -fluciclovine.

Concomitant medications are defined as those with a start date on or after the injection date of ^{18}F -fluciclovine, or those with a start date before the injection date of ^{18}F -fluciclovine but which continued with a stop date on or after the injection date of ^{18}F -fluciclovine.

If medication dates are incomplete and it is not clear whether the medication was concomitant, it will be assumed to be concomitant.

The number and percentage of subjects who took any medications will be presented by center and overall by medication class, standardised medication names sorted in decreasing frequency for all subjects from the SAF, separately for prior medications and concomitant medications.

All prior and concomitant medications will be listed including reported name, medication class, standardised medication name, indication, dose, dose unit, frequency, route of administration, start date and end date or 'ongoing' flag.

4.4.6 Other Subject Characteristics

Not applicable

4.5 Administration of Investigational Product

The volume of undiluted fluciclovine, activity of fluciclovine and injection site reaction during and following fluciclovine administration will be summarised for subjects in the SAF.

All fluciclovine administration data will be listed in full.

5 EFFICACY EVALUATION

All listings will be based on the FAS unless specified otherwise.

5.1 Primary Efficacy Variable

The primary efficacy variable is the change in management plan assessed by comparing pre ^{18}F -fluciclovine PET/CT management plan with the post ^{18}F -fluciclovine PET/CT management plan, for subjects with a positive ^{18}F -fluciclovine PET/CT scan.

5.2 Secondary Efficacy Variables

The secondary efficacy variables are:

- Per subject impact (yes/no) of ^{18}F -fluciclovine PET/CT on pre-PET intended versus post-PET actual subject management
- The rate of detection of any disease site by ^{18}F -fluciclovine PET/CT in the study population
- The rate of detection of:
 - Prostatic bed and other pelvic disease
 - Distant metastases (i.e. bone metastases, visceral metastases or non-regional nodal metastases)with ^{18}F -fluciclovine PET/CT in the study population
- The PPV of ^{18}F -fluciclovine PET/CT to detect regionally recurrent disease compared to adjudication panel decision.
- The PPV of ^{18}F -fluciclovine PET/CT to detect distant metastases compared to adjudication panel decision.

5.3 Definition of Region Levels

Two main regions will be analysed, the prostate and prostate bed and the extra-prostatic region.

The prostate and prostate bed include the following lesion locations:

- Prostate bed left
- Prostate bed right

- Peripheral zone left
- Peripheral zone right
- Central gland left
- Central gland right
- Left seminal vesicle
- Right seminal vesicle

The extra-prostatic regions include the following lesion locations

- Lymph nodes
 - Pelvic lymph nodes
 - Common iliac left
 - Common iliac right
 - Internal iliac left
 - Internal iliac right
 - External iliac left
 - External iliac right
 - Obturator left
 - Obturator right
 - Pre-sacral left
 - Pre-sacral right
 - Peri-rectal anterior
 - Peri-rectal posterior
 - Inguinal left
 - Inguinal right
 - Retroperitoneal lymph nodes
 - Para-aortic
 - Retro-aortic
 - Para-caval
 - Retro-caval
 - Aorto-caval
 - Retrocrural left
 - Retrocrural right
 - Other lymph nodes
 - Intra-peritoneal
 - Mediastinal left
 - Mediastinal right
 - Axillary left
 - Axillary right
 - Cervical left
 - Cervical right
- Soft tissues/parenchyma
 - Lung upper lobe left
 - Lung upper lobe right
 - Lung middle lobe left
 - Lung middle lobe right
 - Lung lower lobe left
 - Lung lower lobe right

- Brain left
- Brain right
- Liver left
- Liver right
- Spleen
- Subcutaneous/cutaneous
- Muscle
- Bowel
- Bones
 - Skull
 - Skull base/maxilla left
 - Skull base/maxilla right
 - Mandible left
 - Mandible right
 - Neck
 - Vertebra C1
 - Vertebra C2
 - Vertebra C3
 - Vertebra C4
 - Vertebra C5
 - Vertebra C6
 - Vertebra C7
 - Vertebra T1
 - Vertebra T2
 - Vertebra T3
 - Vertebra T4
 - Vertebra T5
 - Vertebra T6
 - Vertebra T7
 - Vertebra T8
 - Vertebra T9
 - Vertebra T10
 - Vertebra T11
 - Vertebra T12
 - Vertebra L1
 - Vertebra L2
 - Vertebra L3
 - Vertebra L4
 - Vertebra L5
 - Sacrum left
 - Sacrum right
 - Sacrum central
 - Chest
 - 1st rib left
 - 1st rib right
 - 2nd rib left
 - 2nd rib right
 - 3rd rib left
 - 3rd rib right
 - 4th rib left
 - 4th rib right
 - 5th rib left
 - 5th rib right

- 6th rib left
- 6th rib right
- 7th rib left
- 7th rib right
- 8th rib left
- 8th rib right
- 9th rib left
- 9th rib right
- 10th rib left
- 10th rib right
- 11th rib left
- 11th rib right
- 12th rib left
- 12th rib right
- Sternum
- Clavicle left
- Clavicle right
- Scapula left
- Scapula right
- Pelvis
 - Ilium left
 - Ilium right
 - Superior pubic ramus left
 - Superior pubic ramus right
 - Inferior pubic ramus left
 - Inferior pubic ramus right
 - Pubic body left
 - Pubic body right
 - Ischium left
 - Ischium right
- Appendicular
 - Proximal humerus left
 - Proximal humerus right
 - Proximal femur left
 - Proximal femur right

5.4 Statistical Analysis

5.4.1 Primary Efficacy Analysis

The primary efficacy analysis will be based on the EAS and will be repeated on the PPS as a secondary analysis. Comparisons between the original treatment plan and the revised treatment plan will be categorised as no change, major change or other change. The definitions of the change categories are listed below.

- No change: the original treatment plan is the same as the revised treatment plan
- Major change: the original treatment plan is not the same as the revised treatment plan and the grouping for the original treatment plan is not the same as the grouping for the revised treatment plan

These will be further split and presented according to the following categories:

- Salvage or Non-curative systemic therapy to Watchful waiting
 - Salvage therapy to Non-curative systemic therapy
 - Non-curative systemic therapy to Salvage therapy
 - Alternative Major change
- Other change: the original treatment plan is not the same as the revised treatment plan but the grouping for the original treatment plan is the same as the grouping for the revised treatment plan

These will be further split and presented according to the following categories:

- Modified RT field plan
- Modified androgen-deprivation regimen
- Alternative Other change

Groupings of treatment plans are detailed in the following table:

Original Treatment Plan	Grouping for Original Tx Plan	Revised Treatment Plan	Grouping for Revised Tx Plan
Was androgen deprivation therapy planned	Androgen Deprivation Therapy	Androgen deprivation therapy	Androgen deprivation therapy
		Active surveillance	Active surveillance
		Chemotherapy	Chemotherapy
Salvage radiotherapy to the prostate bed	Salvage Radiotherapy	Salvage radiotherapy to the prostate bed	Salvage Radiotherapy
Salvage radiotherapy to the prostate bed, with boost to areas guided by conventional imaging		Salvage radiotherapy to the prostate bed, with boost to areas guided by conventional imaging	
		Salvage radiotherapy to the prostate bed with boost to areas guided by fluciclovine (18F) PET/CT	
Salvage radiotherapy to the prostate bed and whole pelvis	Salvage Radiotherapy	Salvage radiotherapy to the prostate bed and whole pelvis	Salvage Radiotherapy

Original Treatment Plan	Grouping for Original Tx Plan	Revised Treatment Plan	Grouping for Revised Tx Plan
Salvage radiotherapy to the prostate bed and whole pelvis, with boost to areas guided by conventional imaging		Salvage radiotherapy to the prostate bed and whole pelvis, with boost to areas guided by conventional imaging	
		Salvage radiotherapy to the prostate bed and whole pelvis with boost to areas guided by fluciclovine (18F) PET/CT	
Salvage cryotherapy		Salvage cryotherapy	
	Salvage Cryotherapy	Salvage cryotherapy with treatment plan guided by fluciclovine (18F) PET/CT	Salvage Cryotherapy
Salvage brachytherapy		Salvage brachytherapy	
	Salvage Brachytherapy	Salvage brachytherapy with treatment plan guided by fluciclovine (18F) PET/CT	Salvage Brachytherapy
Salvage HIFU		Salvage HIFU	
	Salvage HIFU	Salvage HIFU with treatment plan guided by fluciclovine (18F) PET/CT	Salvage HIFU
Salvage prostatectomy		Salvage prostatectomy	
	Salvage Prostatectomy	Salvage prostatectomy with targeted resection /	Salvage Prostatectomy

Original Treatment Plan	Grouping for Original Tx Plan	Revised Treatment Plan	Grouping for Revised Tx Plan
		sampling of fluciclovine (18F) positive areas outside conventional surgical field	
Salvage prostatectomy and limited lymph node dissection		Salvage prostatectomy and limited lymph node dissection	
		Salvage prostatectomy and limited lymph node dissection with targeted resection / sampling of fluciclovine (18F) positive areas outside surgical field	
Salvage prostatectomy and extended lymph node dissection (including internal and external iliac, and obturator nodes)		Salvage prostatectomy and extended lymph node dissection (including internal and external iliac, and obturator nodes)	
		Salvage prostatectomy and extended lymph node dissection (including internal and external iliac, and obturator nodes) with targeted resection / sampling of fluciclovine (18F) positive areas outside surgical field	
		Targeted salvage treatment of fluciclovine (18F)	Targeted salvage treatment

Original Treatment Plan	Grouping for Original Tx Plan	Revised Treatment Plan	Grouping for Revised Tx Plan
		positive extra-pelvic / bony areas	
		Other	Other

The classification and sub-classification of change in treatment management plan will be agreed prior to data base lock.

The number, percentage and exact 95% confidence interval (CI) of subjects with and without a change in management plan after ¹⁸F-fluciclovine PET/CT scan results become available will be presented for the EAS. In addition, the number and percentage of subjects with changes categorised as major or other will be presented along with its 95% CI. These summaries will be repeated separately for subjects with a positive and a negative ¹⁸F-fluciclovine PET/CT scan and for subjects without prostatectomy and with prostatectomy. All these summaries will be repeated using the PPS.

Details of the intended management plan, revised management plan and categorisation of change in management plan will be listed.

